#### **8.1.5. Pre-existing Condition**

A preexisting condition is one that is present at the start of the study. A pre-existing condition should be recorded as an adverse event if the frequency, intensity, or the character of the condition worsens during the study period.

At screening, any clinically significant abnormality should be recorded as a preexisting condition. At the end of the study, any new clinically significant findings/abnormalities that meet the definition of an adverse event must also be recorded and documented as an adverse event.

#### **8.1.6. Abnormal Laboratory Values**

A clinical laboratory abnormality should be documented as an adverse event if any one of the following conditions is met:

- The laboratory abnormality is not otherwise refuted by a repeat test to confirm the abnormality
- The abnormality suggests a disease and/or organ toxicity
- The abnormality is of a clinically significant degree requiring active management; e.g. change of dose, discontinuation of the drug, more frequent follow-up assessments, further diagnostic investigation, etc.

#### **8.1.7. Hospitalization, Prolonged Hospitalization or Surgery**

Any adverse event that results in hospitalization or prolonged hospitalization should be documented and reported as a SAE unless specifically instructed otherwise in this protocol. Any condition responsible for surgery should be documented as an AE if the condition meets the criteria for an adverse event.

Neither the condition, hospitalization, prolonged hospitalization, nor surgery are reported as an AE in the following circumstances:

- Hospitalization or prolonged hospitalization for diagnostic or elective surgical procedures for a preexisting condition (e.g., colonoscopy, SCI annual evaluation, respite care).
- Surgery should not be reported as an outcome of an adverse event if the purpose of the surgery was elective or diagnostic and the outcome was uneventful.
- Hospitalization or prolonged hospitalization required to allow efficacy measurement for the study.
- Hospitalization or prolonged hospitalization for therapy of the target disease of the study, unless it is a worsening or increase in frequency of hospital admissions as judged by the clinical investigator.

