#### **8.1.2. Serious Adverse Event (SAE)**

Adverse events are classified as serious or non-serious. A serious adverse event is any AE that:

- results in death;
- is life-threatening (places the subject at immediate risk of death from the event as it occurred);
- results in inpatient hospitalization or prolongation of existing hospitalization;
- results in a persistent or significant disability/incapacity;
- results in a congenital anomaly/birth defect; or
- based upon appropriate medical judgment, may jeopardize the subject's health and may require medical or surgical intervention to prevent one of the other outcomes listed in this definition (examples of such events include allergic bronchospasm requiring intensive treatment in the emergency room or at home, blood dyscrasias or convulsions that do not result in inpatient hospitalization, or the development of drug dependency or drug abuse).

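### Section 8.1.7 leaves a worsened non-target pre-existing condition unreported when it leads to an elective or diagnostic admission, although section 8.1.5 makes it an adverse event

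*Combined protocol and SAP*

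**What the plan says.** Four rules in section 8.1 of the protocol bear on this point.

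- **8.1.5, pre-existing conditions.** Such a condition "should be recorded as an adverse event if the frequency, intensity, or the character of the condition worsens during the study period". There is no exception for the type or urgency of any procedure that follows.
- **8.1.2, seriousness.** An AE is serious if, among other criteria, it "results in inpatient hospitalization or prolongation of existing hospitalization".
- **8.1.7, opening paragraph.** An AE leading to admission is reported as an SAE, except where the protocol specifically directs otherwise. A condition that leads to surgery is documented as an AE if it meets the AE criteria.
- **8.1.7, exclusion list.** The lead-in is "Neither the condition, hospitalization, prolonged hospitalization, nor surgery are reported as an AE in the following circumstances". The first item is "Hospitalization or prolonged hospitalization for diagnostic or elective surgical procedures for a preexisting condition", with routine examples such as colonoscopy and respite care. The second is "Surgery should not be reported as an outcome of an adverse event if the purpose of the surgery was elective or diagnostic"; it applies only if the surgery passed without event. The third concerns admissions needed for efficacy measurement and does not matter here. The fourth excludes admissions for treating the target disease, "unless it is a worsening or increase in frequency of hospital admissions as judged by the clinical investigator".

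The Study Summary admits participants aged 18 to 75 whose chronic diseases, with coronary artery disease as an example, are clinically stable. It also lists product safety as an objective.

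**The concern.** The lead-in to the 8.1.7 list removes the condition itself from AE reporting, not only the admission or the operation. The first item then applies that removal to every elective or diagnostic admission for a pre-existing condition, whether or not the condition deteriorated after treatment began. Section 8.1.5 says the opposite about a condition that deteriorated, and no order of precedence between the two sections is stated.

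What is at stake is consistent classification. One staff member working from 8.1.5 and another working from 8.1.7 could code the same event differently. An event classified out would be missing from the AE log (8.2). If the admission met the SAE definition, it would also be missing from the SAE report that 8.3 sends to the IRB, the R&D Committee and the DSMB.

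**Working it through.** No arithmetic applies and the plan states no figure to reproduce. The check sets the rules side by side and runs cases through them.

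**Case A: a non-target condition.** A participant enters with stable coronary disease, which the Study Summary allows. It worsens on study and leads to a scheduled admission for a diagnostic or elective procedure.

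1. Under 8.1.5 the condition existed at entry and its intensity increased, so it is an AE.
2. Under 8.1.2 an AE that results in inpatient admission is serious.
3. Under the first item of the 8.1.7 list, the admission is for a pre-existing condition and the procedure is diagnostic or elective. The item applies, and it has no worsening exception.
4. Under the lead-in, neither the condition nor the admission is then reported as an AE. This contradicts step 1.
5. The SAE rule in 8.1.7 yields to specific contrary instructions, and the first item is one. The SAE report in step 2 can therefore be lost.
6. The sentence before the list keeps a condition that leads to surgery as an AE if it meets AE criteria. If Case A involves surgery, that sentence and the lead-in conflict within 8.1.7. If the admission is purely diagnostic, the sentence does not reach it.

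**Case B: the same condition, elective surgery, second item only.** This item concerns surgery as the outcome of an AE, so it presupposes that an AE exists. By its own words it drops only the surgery, and only if the surgery was uneventful. The condition would be lost only if the lead-in were applied to an item that does not fit it grammatically. This is an ambiguity, not a clear exclusion.

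**Case C: a study keloid that grows.** The keloid is the target disease, so for an admission the fourth item is the specific rule, and it excepts worsening. Excision without admission falls outside the first and fourth items, which both concern admissions. It meets the second item (Case B) and the sentence before the list, which keeps the condition as an AE.

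**Result.** Only Case A gives a clear contradiction with 8.1.5. The fourth item shows that a worsening exception was thought necessary for the target disease. The broader first item lacks it.

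**The case against.** The strongest reply is that 8.1.7 already protects the condition. The sentence before the list keeps a condition responsible for surgery as an AE if it meets AE criteria, and a worsened condition does so under 8.1.5. The first item's examples suggest routine care, not treatment of deterioration on study. Related, unexpected events that suggest greater risk also keep their own reporting route as unanticipated problems (8.1.3 and 8.3), whatever 8.1.7 says.

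Much of this stands, and it limits the point. It does not remove it. The list follows the protective sentence and contradicts it, the first item also covers diagnostic admissions, and its examples illustrate the item without restricting it. The unanticipated-problem route needs all three of its criteria, so a worsening judged expected or unrelated would not qualify.

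A reader might infer more than the documents support:

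- **That 8.1.7 conceals the growth and excision of a study keloid.** The fourth item excepts worsening, and keloid area and height are the primary outcome, measured monthly. Section 4.4.2 also seeks final images and measurements at withdrawal. Some ambiguity remains, because that exception rests on investigator judgement and could be read as referring to admissions. Growth would still appear in the efficacy data.
- **That every elective procedure removes the condition.** The first item covers admissions only, and the second drops only uneventful surgery.
- **That 8.1.7 contradicts 8.1.2.** It does not. Section 8.1.7 states how its SAE rule yields to the list.
- **That the stopping provision in 8.6 would be bypassed.** It concerns study-related events, and an unrelated scheduled admission would not plainly trigger it.
- **That one lost event shifts the rate by 1/5 = 20 percentage points.** That is true of any event among five people and says nothing about this wording. Five is also the completer target. Withdrawn participants may be replaced (4.4.2), so more may be treated.

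**Conclusion.** The point holds in a narrow form and is minor. Read literally, the lead-in and first item of 8.1.7 leave unreported a non-target pre-existing condition that worsens on study and leads to an elective or diagnostic admission. That contradicts 8.1.5. It is also out of step with the sentence before the list, where surgery is involved, and with the fourth item. The SAE report can be lost with it.

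The size cannot be given as a number, because the documents do not say how often such admissions would occur. The conclusion assumes that staff apply the list as written and that no separate instruction gives 8.1.5 precedence; the protocol states none. It does not depend on the study keloids or on any effect on trial stopping. It merits correction because safety is a stated objective and the remedy is a few words.

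**What to change.** Three wording changes in 8.1.7:

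1. Add to the first item an exception for a condition whose frequency, intensity or character has worsened since study entry, matching the test in 8.1.5.
2. State that 8.1.5 takes precedence over the 8.1.7 list, so that a worsened pre-existing condition is recorded as an AE whatever the procedure that follows.
3. Clarify that the second item removes only the uneventful elective or diagnostic surgery as an outcome, not the underlying AE.

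Limiting the first item to procedures planned before the first application is an optional drafting choice and is not needed to remove the contradiction.

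The cost is a short wording amendment. Design, sample size and visit procedures are unaffected. The reported AE or SAE count may be slightly higher.

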### **8.2. Recording of Adverse Events**

At each contact with the subject, the investigator or study staff will seek information about adverse events by specific questioning and, if appropriate, by examination. Information on all AEs will be recorded immediately in the source documentation. Site staff will record AEs using the appropriate data collection form in REDCap, which will be exported as an AE Log (See Section 9.3) for periodic review, at least monthly and ad hoc, depending on severity and expected/unexpected nature of the event.

The clinical course of each event will be followed until resolution, stabilization, or until it has been determined that the study treatment or participation is not the cause. SAEs that are still ongoing at the end of the study period will be followed up to determine the final outcome. Any SAE that occurs after the study period and is considered to be possibly related to the study treatment or study participation will be recorded and reported per Institutional policy and according to FDA requirements.

### ***8.3. Reporting of Serious Adverse Events and Unanticipated Problems***

SAEs and UPIRSOs will be reported per local IRB policy and procedure.

Each subject is evaluated for any adverse events (AE). Any event that is reported to either the principal investigator or designated research staff by either the subject or medical staff caring for the subject and which meets the criteria will be documented. Any AE reported as serious will necessitate an adverse event report, which will be submitted to the IRB, R&D Committee, and to the Pepper Center DSBM.

Unanticipated risks to subjects or others (UPIRSO) that are a result of study participation are promptly reported to the IRB, the VA R&D Committee, and, if deemed appropriate, to the Pepper Center DSMB. The report will include a description of the event, when and how it was reported, as well as any official chart records or documentation to corroborate the event or the reporting of the event. All adverse events will be graded as mild, moderate, or severe. All adverse events will be summarized annually and submitted to the IRB and R&D Committees. Any action resulting in a temporary or permanent suspension of this study (e.g. local site IRB actions) will be reported to FDA or drug manufacturer per IRB stipulations.

### 8.3.2. Investigator reporting: notifying the UTHSCSA IRB

## Notifying the IRB and or FDA if SAE or UPIRSO

- *Within 7 calendar days*

Any study event that is:

- associated with the use of the study drug
- unexpected,
- fatal or life-threatening, and

- *Within 15 calendar days*

Any study event that is:

- associated with the use of the study drug,
- unexpected, and
- serious, but not fatal or life-threatening

-or-

- a previous adverse event that was not initially deemed reportable but is later found to fit the criteria for reporting (reporting within 15 calendar days from when event was deemed reportable).

Any finding from tests in laboratory animals that:

- suggests a significant risk for human subjects including reports of mutagenicity, teratogenicity, or carcinogenicity.

### **8.4. Medical Monitoring**

The Investigator and or Co-PI will review the safety and progress of this study on a monthly basis or when needed if SAE or SAE-UPIRSO occurs.

### **8.5. Investigator Reporting of Protocol Deviations/Violations**

Departures during the conduct of a research study constitute a protocol deviation, violation or exception and as such must be reported to the UTHSCSA IRB.

Tracking and reporting of protocol deviations and violations to the IRB is the responsibility of the PI. To determine whether deviations or violations require prompt reporting or other action, refer to the IRB document entitled “Decision Tree – Evaluating Departures” on the IRB website. Failure to report departures from the protocol according to IRB policy may constitute possible non-compliance, which will require a Prompt Report Form and possible FDA reporting by IRB.

#### **8.5.1. Deviations and violations may be identified in a number of ways including:**

- A report by an individual can be made directly to the IRB Office.
- The IRB may learn of event through its continuing review of ongoing research.
- Compliance reviews (audits) conducted by the Office of Regulatory Affairs and Compliance or one of the HSC affiliated institutional compliance offices.
- A report by an individual can be made directly to the Office of Regulatory Affairs and Compliance (Hotline) or one of the HSC affiliated institutional compliance offices.
- A report by another committee, department, institution, or official.
- An audit or report from the study sponsor or sponsor’s monitoring entity.

#### **8.5.2. Definitions of Protocol Deviations/Violations**

- Protocol deviations – such as out of window visit, missed lab, usually recognized after the fact, etc.
- Protocol violations – enrolling an ineligible participant, using wrong consent version, willful act of

- not following protocol
- Emergency violations Refer to UTHSCSA IRB Policy website:  
<https://research.uthscsa.edu/irb/policy/deviations> for more information

## **8.6. Stopping Rules**

Should a subject develop a rash during study intervention, RAPA medication will be stopped and their participation will cease.

Should a female participant of childbearing age become pregnant during study intervention, RAPA medication will be stopped and participation will be withdrawn.

In the unlikely event that a study-related death or SAE occurs, the decision to stop the trial, either temporarily or permanently, will be the collaborative responsibility of the Pepper Center DSMB and the Principal Investigator.

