##### **4.4.2. Data Collection and Follow-up for Withdrawn Subjects**

If a subject withdraws consent to participate in the study, attempts will be made to obtain permission and capture final photographic images of the keloids and measurement before being disenrolled.

If subjects are withdrawn prematurely from the study, Principal Investigator will consult with Study Statistician about handling any incomplete data set as compared to the full data set that fully supports the analysis. The Principal Investigator will determine whether to replace the withdrawn subject to achieve the goal of 5 completers.

Lost to follow up (LTFU) will be defined as a subject not answering or responding to 2 or more consecutive phone follow up calls after starting study medication, or after returned-receipt of 1 certified letter concerning discontinuation of participation in the study.

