## 6.7. Visit 7 (approximately 4 weeks after Visit 6) – Month 6 – Final Study Visit

We will ask participants to return to the hospital to undergo post-treatment procedures, conclude the study data collection and disenrollment processing.

- Vital signs, weight, and lab work to ensure safety or rule out systemic infection or effects (CBC, CMP, lipid panel)
- Update medical history, concomitant medications, focused physical examination, and
- Evaluation of medication compliance
- Final adverse event review
- Keloid observation and clinical assessment
- Photography and caliper measurements – (same as baseline)

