## 6.8. Summary Visit Schedule

Event	Screening & Baseline Visit 1	Visit 2 (V1 +1m)	Visit 3 (V2 +1m)	Visit 4 (V3 +1m)	Visit 5 (V4 +1m)	Visit 6 (V5 +1m)	Visit 7 (V6 +1m)
Consent	X						
Vital signs	X	X	X	X	X	X	X
Height (V1 only) and weight	X						X
CLOX exam	X						
Urine HCG, monthly	X	X	X	X	X	X	
Labs: CBC, CMP, and lipid panel	X			X			X
History	X						X
Physical Exam	X						X
ConMed Review	X	X	X	X	X	X	X
Keloid Observed		X	X	X	X	X	X
Photo and Caliper		X	X	X	X	X	X
Dispensing Rx		X	X	X	X	X	
Medication Instructions and phone calls weekly between V1-V2 and at midpoint between V2-7 for compliance monitoring		X	X	X	X	X	
AE Review			X	X	X	X	X
Questionnaires		X					X
Disenrollment							X

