## **8. Safety and Adverse Events**

### **8.1. Definitions**

#### **8.1.1. Adverse Event (AE)**

In general, AE is used very broadly and encompasses physical and psychological harms and includes:

Any untoward or unfavorable medical occurrence in a human subject, including any abnormal sign (for example, abnormal physical exam or laboratory finding), symptom, or disease, temporally associated with the subject's participation in the research, whether or not it is considered related to the subject's participation in the research.

Intercurrent illnesses or injuries should be regarded as adverse events. Abnormal results of diagnostic procedures are considered to be adverse events if the abnormality:

- results in study withdrawal
- is associated with a serious adverse event
- is associated with clinical signs or symptoms
- leads to additional treatment or to further diagnostic tests
- is considered by the investigator to be of clinical significance

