#### **8.1.4. Adverse Event Reporting Period**

The study period during which adverse events must be reported is normally defined as the period from the initiation of any study procedures to the end of the study treatment follow-up. For this study, the study treatment follow-up is defined as 30 days following the last administration of study treatment.

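### No urine pregnancy test is scheduled at Visit 7, so the sixth treatment month is not followed by one

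*Combined protocol and SAP*

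**What the plan says.** Section 4.1 requires a negative pregnancy test at entry. Once treatment has begun, Section 8.6 applies: "Should a female participant of childbearing age become pregnant during study intervention, RAPA medication will be stopped and participation will be withdrawn."

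The tests that would trigger that rule are set out twice.

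- **Visit narrative (6.1 to 6.7).** A urine test is listed at Visits 1, 2, 3, 5 and 6, and at Visit 4 through its reference back to the preceding visit. The Visit 7 entry neither refers back nor lists a pregnancy test. Its laboratory item reads "Vital signs, weight, and lab work to ensure safety or rule out systemic infection or effects (CBC, CMP, lipid panel", and that completes the list.
- **Schedule table (6.8).** The row labelled "Urine HCG, monthly" is marked at Visits 1 to 6 and blank at Visit 7.

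Treatment is once daily for 6 months (3.2, 5.2). Ointment is dispensed at Visit 1 by the narrative in 6.1.2 and at Visits 2 to 6 by the table, and not at Visit 7. On adverse events, 8.1.4 says that "the study treatment follow-up is defined as 30 days following the last administration of study treatment".

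**The concern.** The narrative and the table agree, so the blank at Visit 7 is not a damaged table cell. Ointment handed out at Visit 6 is applied until Visit 7. A participant who conceives in that month has been exposed, yet she is disenrolled at Visit 7 without a test.

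Product safety is a stated objective in the Study Summary, and an on-treatment pregnancy is an event the protocol cares about enough to end participation. The reassurance about systemic exposure comes from Section 1.3, where no blood level was detected with the 8% ointment over at most about 7 days, against 6 months here. The scheduled laboratory work includes no rapamycin level, so the trial will not itself confirm that exposure stays local. What is at stake is knowing about an exposed pregnancy. No efficacy endpoint or analysis is touched.

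**Working it through.** The protocol gives no figure for this gap, so there is none to reproduce.

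**Inputs from the protocol.** Visits are about 4 weeks apart (6.2 to 6.7), taken as 28 days. Treatment runs from Visit 1 to Visit 7. Tests fall at Visits 1 to 6.

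**Input assumed.** A urine test turns positive L days after conception, with L = 14 and a range of 10 to 21. The documents do not give this.

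**Step 1: the calendar.** Visit k falls on day 28 × (k − 1).
- Visit 6: 28 × 5 = day 140, the last test.
- Visit 7: 28 × 6 = day 168, the end of treatment.

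**Step 2: treatment time after the last test.** 168 − 140 = 28 days, and 28/168 = 16.7%. This needs no assumption about the lag.

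**Step 3: allowing for the lag.** A test on day t can find conceptions up to day t − L. The treatment days on which a conception escapes every scheduled test are:
- as planned: 168 − (140 − L) = 28 + L
- with a Visit 7 test: 168 − (168 − L) = L

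| Lag L | As planned | With a Visit 7 test | Difference |
|---|---|---|---|
| 10 days | 38 (22.6%) | 10 (6.0%) | 28 |
| 14 days | 42 (25.0%) | 14 (8.3%) | 28 |
| 21 days | 49 (29.2%) | 21 (12.5%) | 28 |

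The difference is (28 + L) − L = 28 days whatever the lag. The missing test therefore accounts for 28 of 168 days. The other L days are out of reach of any test done on the last day of treatment. With L = 14, the added test would find conceptions from day 126 to day 154 and miss those from day 154 to day 168.

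**Step 4: other routes of detection in the sixth month.**
- Section 5.4 puts a call midway between Visits 6 and 7, near day 154.
- Section 6.7 has an updated history, a focused examination and a final adverse-event review at Visit 7.
- Section 8.1.4 keeps reporting open for 30 days after the last application, but 6.8 schedules no visit or call in that window.

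Each route depends on the participant knowing and saying that she is pregnant, or on an examination finding it at a very early stage.

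**The case against.** The schedule has a coherent logic. Tests fall at exactly the visits where drug is dispensed, so every month's supply, including the sixth, is preceded by a negative test. Six tests over six treatment months fits the label in the table. At Visit 7 there is no drug left to withhold, so a test there cannot serve the stopping rule. All of this stands: the schedule is not self-contradictory, and an exit test is an improvement, not the correction of an error. What remains is that testing before supply says nothing about exposure after the last supply, and the other routes do not involve a test.

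Two stronger readings are tempting.

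**That 25% of treatment goes uncovered.** The 42 days behind that figure include 14 that stay uncovered after the fix and rest on an assumed lag. The omission itself accounts for 28 days. A share of days is also not a risk: the number of participants who can become pregnant is not given.

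**That the trial would drop an exposed pregnancy without learning its outcome.** A reader might infer this because 8.6 ends participation, 8.1.4 closes reporting at 30 days, and 4.4.2 speaks mainly of data handling: "If subjects are withdrawn prematurely from the study, Principal Investigator will consult with Study Statistician about handling any incomplete data set". The documents do not support it.
- Section 8.1.1 makes an abnormal diagnostic result an adverse event if it "results in study withdrawal", and 8.6 makes withdrawal mandatory.
- Section 8.2 then applies: "The clinical course of each event will be followed until resolution, stabilization". It also provides for recording "Any SAE that occurs after the study period and is considered to be possibly related to the study treatment", and 8.1.2 counts a birth defect as serious.
- Withdrawal under 8.6 is not withdrawal of consent, so later contact is not ruled out.
- The consent form and Section 8.3.1, which the contents list names, are not in the available text and may deal with pregnancy directly.

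This cover is imperfect. It depends on treating a positive test as an abnormal result, and 8.2 allows follow-up to end once treatment is judged not to be the cause. That justifies a clarifying sentence, not a finding that follow-up is absent.

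**Conclusion.** The gap is real but small. No scheduled pregnancy test follows the sixth treatment month, about 28 of 168 days (17%), and the narrative and the table both show it. That size rests only on visits 28 days apart and treatment running to Visit 7. A pregnancy begun in that month may still come to light, but only by self-report or examination.

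It is a desirable improvement and no more. Few participants are planned, an event is unlikely, preliminary work found no detectable blood level over short use, and no efficacy result depends on it.

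**What to change.** Add a urine pregnancy test at Visit 7, for participants who can become pregnant, to the Visit 7 list in Section 6.7 and to the table in Section 6.8. State that its purpose is to identify pregnancies exposed to the study drug. State also that it will not find conceptions in roughly the last two weeks (10 to 21 days on the assumed lag), so that a negative result is not over-read.

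The cost is one more run of a test already done monthly, at a visit that already includes laboratory work, plus a minor amendment for IRB approval.

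Optionally, add a sentence to 8.6 saying that a pregnancy begun on treatment is followed to its outcome, with the participant's agreement. It is unnecessary if the consent form or the rest of the safety-reporting section already says so. The stopping rule itself needs no change.
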